8.1.1 Recruitment and Retention Efforts

Study enrollment will be monitored closely and include a mitigation plan if recruitment goals are lagging. Steps to help meet enrollment targets include, but are not limited to: adding additional study sites and performing 'booster monitoring visits' with non-enrolling or under-enrolling sites. Enrollment reports will be generated on a regular basis and shared with sites to inform target goals and implement any new strategies based on results.

Retention efforts to minimize loss to follow-up and missing data will include, but are not limited to:

- Judicious electronic case report form (eCRF) design to minimize length and enhance ease of use
- Comprehensive site staff training emphasizing the importance of data collection through the end of follow-up, even if the patient discontinues ocrelizumab
- Engaging healthcare providers (HCPs) with a good track record for both enrollment and retention of patients
- Promote HCP engagement through regular registry updates including best practice guidance and scientific exchanges
- Updating contact information at each patient encounter
- Close monitoring of data collection throughout the study
- Collect informed consent for continuous patient follow-up, even after leaving the initially associated study site

8.1.2 Rationale for Study Design

Data collected from clinical studies with ocrelizumab provide a sound body of evidence on its efficacy and safety in the treatment of RMS and PPMS. Although randomized controlled trials (RCTs) are the 'gold standard' for generating evidence of these data, enrolment criteria, short observation periods, and low patient numbers limit relevance to standard clinical practice.

Data on the utilization and the treatment outcomes of ocrelizumab under clinical practice conditions in a large, unselected patient population still need to be elicited to obtain an overview not only on the incidence of expected AEs but also of uncommon and unexpected AEs. Therefore, only a study performed in a real life setting can help fill this knowledge gap between clinical trials and clinical practice.

8.2 SETTING

8.2.1 Centers

This study will be conducted at approximately 250 centers specialized in MS covering all regions of Germany.

8.2.2 Study Population

This study will enroll patients with MS from the post-marketing setting who have initiated treatment with ocrelizumab no more than 30 days prior to baseline visit. The decision of the treating physician to prescribe ocrelizumab must have been made for the patients beforehand and independent of participation in this study.

Patients must meet the following criteria for study entry:

- signed informed consent
- have a diagnosis of MS
- aged 18 years or older
- newly treated with ocrelizumab (within 30 days prior to enrollment) according to the local label

Patients who meet any of the following criteria will be excluded from study entry:

 active participation in other interventional and non-interventional studies investigating DMTs for MS

Patients receiving treatment for MS with Ocrelizumab (OCREVUS®) according to standard of care and in line with the current summary of product characteristics (SPC) / local labeling and who have no contraindication to ocrelizumab therapy as per the local label are eligible for observation in this study if written informed consent is provided.

Enrollment of patients will be conducted to ensure 60% of the study population is female in order to adequately power breast cancer event rates in the global PAS studies (BA39730 & BA39731). Sites will be required to maintain a patient screening log of eligible patients reviewed for participation at their treatment centers. This log will document how patients were included or excluded from the study in order to assess the representativeness of the study population.

8.2.3 Prior and Concomitant Medication and Treatment

Prior and concomitant medications and treatments at the beginning of the study or introduced during the study will be collected as following:

- All previous treatments and therapies for MS, including their duration (start/stop dates)
- All other prior and concomitant immunomodulatory and immunosuppressive treatments including their duration (start/stop dates)
- Other previous and ongoing medications: from 3 months prior to enrollment only

8.2.4 Dosage, Administration, and Compliance

Dosing and treatment duration of ocrelizumab collected as parts of this noninterventional study are at the discretion of the physician in accordance with local clinical practice and local labeling.

8.3 VARIABLES

8.3.1 Primary Safety Outcome Measures

The primary outcome measure for this study is as follows:

 incidence and type of uncommon AEs (i.e. AEs with an incidence rate of at least 0.1% [1 out of 1000 patients] at least once) and death with primary and underlying causes in patients with MS newly exposed to ocrelizumab

8.3.2 Secondary Outcome Measures

The secondary outcome measures for this study are as follows:

- long-term effectiveness
 - treatment success (proportion of patients with no clinical disease activity measured by relapse and disease progression and no treatment discontinuation due to adverse events [excluding pregnancies] and lack of effectiveness)
 - o proportion of patients with relapses
 - proportion of patients with confirmed disability progression (CDP)
 - o time to onset of CDP
 - o time to onset of confirmed disability improvement (CDI)
 - o Patient reported Outcomes: treatment satisfaction
- other safety endpoints:
 - o incidence of all adverse events
 - o incidence of serious infections
 - o incidence of malignancies
 - o mortality rate due to malignancies

Exploratory Outcome Measures

The exploratory outcome measures for this study are as follows:

- · change from baseline in magnetic resonance imaging (MRI) lesions
- change from baseline in global impression on the disease course as reported by physician and patient using the 'Clinical Global Impression (CGI)' scale

 change from baseline in pharmacoeconomic outcomes as measured by 'Work Productivity and Activity Impairment Questionnaire: Multiple Sclerosis (WPAI:MS)'

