- · Vital signs (BP, HR, body temperature) and weight
- Laboratory parameters, if available:
 - Blood cell count (RBC, hemoglobin, hematocrit, absolute and differential WBC, ANC, quantitative platelet count)
 - o Immunoglobuline levels (IgG, IgM, IgA)
 - o Liver enzymes (ALT, AST, gamma-GT
 - o Renal status (creatinine, BUN, urinalysis)
 - Clinical chemistry (alkaline phosphatase, amylase, total bilirubin, urea, uric acid, random glucose, potassium, sodium)
 - Flow cytometry (B-cell depletion and recovery [CD19+] and T-cell counts [CD3+, CD4+, CD8+])
- · Continuation of therapy or reason for discontinuation, if applicable
- Concomitant medications
- MS specific symptoms and treatment, relapses:
 - MS relapse during the treatment period (start/end dates)
 - Most recent EDSS score since the last encounter, if available
 - Most recent MRI results since the last encounter, if available
 - MS treatment changes and rationale

- Clinical management questions during study:
 - Gynecological consultation
 - o Breast check
 - Dermatological check
 - Malignancy/cancer detection tests (e.g., mammography, Pap test, colonoscopy, laboratory malignancy markers)
- Pregnancy status, if applicable (patient-reported, female patients)
- Safety assessments:
 - all AEs
 - SAEs
 - pregnancies
 - any malignancies, including but not limited to MedDRA Standardized MedDRA Queries (SMQ) of malignant or unspecified tumors, and non-melanoma skin cancers (NMSCs)
- Malignancy information, if applicable (questionnaire regarding in-depth malignancy information will be solicited from the patient's treating physician or oncologist [only collected if a malignancy is identified]), including, but not limited to:
 - Cancer type
 - Diagnosis date
 - Location of primary tumor
 - o Tumor grade
 - Stage at diagnosis
 - Action taken with ocrelizumab therapy at the point of diagnosis
 - AEs of special interest (AESIs):
 - Cases of potential medicine-induced liver injury that include an elevated ALT or AST in combination with either an elevated bilirubin or clinical jaundice, as defined by Hy's law (see Appendix 3).
 - Suspected transmission of an infectious agent by the study medicine (STIAMP)
 - Death information, if applicable (e.g., date of death, primary and underlying causes of death as entered for the AE)
- Ocrelizumab administration information (e.g., dates of administration [stop and restart dates, if applicable], dose, dosing frequency)
- QoL / PRO:
 - Clinical Global Impression (CGI)

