8.7 DATA ANALYSIS

The statistical analysis will be described in a prospective statistical analysis plan. This plan will summarize all analyses in detail. Statistical analysis will be mainly based on descriptive methods. To check for potential channeling effects various time spans of patients enrolled will be analyzed. No hypothesis testing will be performed in this NIS. All analyses are regarded exploratory in nature.

All available data will be included in the analyses and will be summarized as far as possible. In general, there will be no substitution of missing data, i.e. missing data will not be replaced, missing data will be handled as 'missing' in the statistical evaluation ('observed cases analysis'). All data of patients who withdraw (e.g., who discontinued prematurely) will be documented anonymously and discussed, as necessary, in the clinical study report.

Generally, all safety analyses will be presented separately for the MS types RMS and PPMS patients as well as pooled. Analyses of effectiveness will be prepared by MS type only.

8.7.1 Safety Analyses

Analysis population

The core analysis population consists of all enrolled patients with data available.

The following analysis sets of patients will be used in this study:

- Enrolled Set (ES) defined as all patients recorded in the clinical database
- Safety Set (SS) defined as all patients in the ES treated with at least one dose of studied medicinal product
- Full Analysis Set (FAS) defined as all patients of the SS who had at least one documentation after start of the therapy

The safety analyses will be done for the safety analysis population, the effectiveness analyses will be done for the Full Analysis Set. All other analyses will be done for all enrolled patients.

Handling of deviations from the study protocol will be detailed in the SAP or a separate document. It is planned to organize a Data Review Meeting prior to database hard lock and database freeze for interim analyses. This preanalysis review should cover decisions concerning the exclusions of patients or data from the analysis sets.

Patient Disposition

Tables for disposition will be provided for the ES. A flowchart will show the final disposition of all patients in the different analysis sets according to the treatment cohorts together with a summary of the reasons for exclusion.

Baseline Characteristics and demographics

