8.7.2 Effectiveness Analyses

Effectiveness analyses will be conducted on the Full Analysis Set.

Descriptive analyses of the secondary endpoints will be performed. Secondary variables will be summarized. For continuous data, the mean, standard deviation (SD), median, range (min, max) and interquartile range (Q1, Q3) will be presented. Categorical data will be displayed by absolute and relative frequencies (percentages).

Secondary time-to-event endpoints will be analyzed using Kaplan-Meier product limit methods to estimate the survival distributions and the median time-to-event. The time to endpoint will be defined as an interval between the date of enrolment (date of first visit) and date of first occurrence of the event. For patients who are event free, the censoring time will be calculated as a time interval between date of enrolment and the patient's final contact with available data concerning the event. The estimates and graphical presentation will be performed via Kaplan-Meier approach.

Further analyses will be performed to investigate the validity of results in this non-interventional study, e.g. time-dependent confounding, informative censoring, informative treatment changes/discontinuations, heterogeneity of results, and how to handle missing data. These will be described in the SAP.

Corresponding 95% confidence intervals will be provided, where appropriate.

Full details of the statistical analyses will be described in a SAP.

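### Treatment success and relapse are planned as percentages with no time horizon and no allowance for censoring, so the figures depend on length of follow-up and on how lost patients are handled

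*Protocol*

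**What the plan says.** **Endpoints.** Protocol 8.3.2, repeated in the synopsis, lists "treatment success (proportion of patients with no clinical disease activity measured by relapse and disease progression and no treatment discontinuation due to adverse events" (pregnancies excepted) or lack of effectiveness. It also lists "proportion of patients with relapses" and "proportion of patients with confirmed disability progression (CDP"). None of the three has a time point. "time to onset of CDP" and time to confirmed disability improvement are separate endpoints.

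**Analysis.** Section 8.7.2 states: "Categorical data will be displayed by absolute and relative frequencies (percentages"). Kaplan-Meier, with censoring at the last contact that has data on the event, is reserved there for the secondary time-to-event endpoints. Effectiveness is analysed on the Full Analysis Set (FAS), defined in 8.7.1 as "all patients of the SS who had at least one documentation after start of the therapy". Section 8.7 does not replace missing values: "missing data will be handled as 'missing' in the statistical evaluation ('observed cases analysis').

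**Follow-up.** Section 8.1 gives 30 months of recruitment and 7.5 to 10 years of observation per patient, shortened by death, withdrawal of consent or loss. Observation continues after ocrelizumab is stopped. Section 8.7.4 puts all endpoints into annual interim reports.

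**Relapse collection.** The follow-up and completion lists in 8.4.2 ask for "MS relapse during the treatment period (start/end dates"), and Table 1 footnote j has the same restriction.

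**The concern.** Treatment success is the endpoint through which 7.2 expresses the effectiveness objective. It is defined by the absence of failure, so its value depends on how long each patient was watched. A plain percentage over unequal follow-up mixes patients seen for months with patients seen for ten years and has no stated horizon. Successive interim figures would not be comparable with each other. RMS and PPMS figures would not be comparable if retention differs between them.

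Two further passages affect who and what is counted.

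- **FAS entry.** Section 8.2.2 allows the first infusion up to 30 days before the baseline visit, so the enrolment record alone could satisfy the FAS rule. Table 1 footnote b places baseline before the first infusion, in which case it could not.
- **Relapses off drug.** The relapse item is tied to the treatment period, while 8.1 and 8.4.2 plan follow-up whether or not the patient stays on drug. Read literally, relapses after stopping would go unrecorded although the patient stays under observation.

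**Working it through.** **The plan's own figures.** The protocol gives no expected value for treatment success, relapse, CDP or dropout, so there is nothing to reproduce for this point. Its safety sample size does reproduce: -ln(0.05)/0.001 = 2995.7, stated as about 3000. It has no bearing here.

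**Inputs from the protocol.** Entry over 2.5 years and administrative follow-up of 7.5 to 10 years (8.1).

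**Assumptions.** Constant failure hazard h of 5% or 10% per year; independent loss hazard d of 3%, 5% or 10% per year; uniform entry.

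**Step 1: growing follow-up, no loss.** At study year t, follow-up is uniform from t - 2.5 to t. The crude percentage is [exp(-h(t - 2.5)) - exp(-ht)]/(2.5h). With h = 0.05 the denominator is 0.125:

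- Year 3: (0.9753 - 0.8607)/0.125 = 91.7%
- Year 5: (0.8825 - 0.7788)/0.125 = 83.0%
- Year 10: (0.6873 - 0.6065)/0.125 = 64.6%

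The hazard never changes; only the mean follow-up does (1.75, 3.75 and 8.75 years).

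**Step 2: loss, at T = 7.5 years.**

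- Kaplan-Meier target: S = exp(-hT)
- Failures observed: F = h/(h+d) × (1 - exp(-(h+d)T))
- Completers without failure: C = exp(-(h+d)T)
- Lost patients kept as event-free: 1 - F
- Lost patients dropped as missing: C/(C + F)

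Example, h = d = 0.05: S = exp(-0.375) = 68.7%; F = 0.5 × (1 - 0.4724) = 0.2638; kept gives 73.6%; dropped gives 0.4724/(0.4724 + 0.2638) = 64.2%.

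| Failure/yr | Loss/yr | Kaplan-Meier | Lost kept as event-free | Lost dropped |
|---|---|---|---|---|
| 5% | 3% | 68.7% | 71.8% | 66.1% |
| 5% | 5% | 68.7% | 73.6% | 64.2% |
| 5% | 10% | 68.7% | 77.5% | 59.1% |
| 10% | 3% | 47.2% | 52.1% | 44.1% |
| 10% | 5% | 47.2% | 55.0% | 41.9% |
| 10% | 10% | 47.2% | 61.2% | 36.5% |

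Keeping lost patients overstates success by about 3 to 14 points; dropping them understates it by about 3 to 11. The two readings differ by up to 61.2 - 36.5 = 24.7 points. With no loss, all three columns agree.

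**Step 3: when the loss effect bites.** For small T the overstatement is about hdT²/2, so it starts near zero. With h = 0.08 and d = 0.05 it is 0.2 points at 1 year and 0.7 at 2 years. Averaged over follow-up of 7.5 to 10 years, it is 58.3% - 49.7% = 8.6 points.

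**The case against.** **Direction of bias.** A reader might infer that lost patients are counted as successes and that effectiveness is always overstated. The protocol does not say so. Its observed-cases rule could equally remove them, and Step 2 shows that this reverses the bias. The objection stands against any one-way claim. It does not rescue the percentage, because both readings miss the target.

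**Early interims.** A reader might also infer that loss does most harm in the early interim reports. Step 3 shows the opposite. The interim problem is the growth of follow-up in Step 1.

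**CDP.** It already has a Kaplan-Meier endpoint, so the gap concerns treatment success and relapse. That stands.

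**Deferral to the SAP.** Section 8.7.2 leaves informative censoring, treatment discontinuation and missing data to the SAP, and the synopsis names time to event among the summaries for effectiveness data. The SAP may therefore close part of the gap. Even so, 8.7.2 presents these as further analyses of validity, while 8.3.2 itself fixes the endpoints as proportions. Nor can an SAP recover relapses that were not collected.

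**Stopping for other reasons.** The definition states openly which discontinuations are failures, and these patients stay under observation. Separate on-treatment and ever-treated versions would be a choice of estimand, not the repair of an error.

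**FAS and relapse wording.** One cannot conclude that patients without follow-up enter the FAS, or that relapses off drug are never recorded. Section 8.4.2 itself uses the treatment period loosely, directly after saying that follow-up continues off drug, and 8.7.1 plans a data review of exclusions. These are conflicts to settle, not demonstrated losses.

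**Conclusion.** The point holds in a limited form. Treatment success and relapse are fixed as proportions with no horizon and no censoring-aware estimate, under follow-up that is unequal by design. Follow-up alone moves the success figure from 91.7% (year 3) to 83.0% (year 5) and 64.6% (year 10) under a constant 5% annual failure rate. With loss, the error at 7.5 years is about +3 to +14 points or about -3 to -11 points, depending on a handling rule that the protocol leaves open.

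All failure and loss rates are assumptions, since the protocol gives none. The upper end is severe: 10% loss per year means 1 - exp(-0.75) = 53% lost by 7.5 years if failures are ignored. Loss is also taken as independent of failure.

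These are secondary, descriptive endpoints in a study whose primary objective is safety. The change should be made, but the primary analysis is not affected.

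**What to change.** 1. Estimate treatment success and freedom from relapse as time to first failure by Kaplan-Meier, censored at the last assessment with data on the component. Report both at fixed yearly landmarks, by MS type, in the interim and final reports.
2. Present the CDP proportion as the landmark estimate from the Kaplan-Meier analysis already planned.
3. State how patients who are lost, and those who stop for reasons outside the failure definition, are handled.
4. Require at least one effectiveness assessment after the enrolment visit for the FAS, and reconcile 8.2.2 with Table 1 footnote b.
5. Reconcile the treatment-period wording for relapses (the 8.4.2 lists and Table 1 footnote j) with follow-up after discontinuation (8.1 and 8.4.2), so that relapses are recorded throughout observation.

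**Cost.** Minor wording and analysis work and no added visits. Whether the eCRF needs changing cannot be judged, because it is not shown. Headline percentages may become less favourable.

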Ocrelizumab is a recombinant, humanized monoclonal antibody that selectively targets CD20-expressing B cells and showed positive effects in different forms of multiple sclerosis (MS). Two identical, randomized, active-controlled studies (OPERA I [Study WA21092] and OPERA II [Study WA21093], Hauser et al. 2017) demonstrated superior efficacy outcomes of ocrelizumab versus interferon beta-1a in relapsing forms of multiple sclerosis (RMS). One randomized placebo-controlled study (ORATORIO [Study WA25046], Montalban et al. 2017) demonstrated superior efficacy of ocrelizumab versus placebo in primary progressive multiple sclerosis (PPMS). The safety profile of ocrelizumab was consistent between the RMS and PPMS studies. The proportions of patients with adverse events (AEs) or serious adverse events (SAEs) were similar in the ocrelizumab, interferon beta-1a (OPERA I & II) or placebo groups (ORATORIO), respectively. Infusion-related reactions and mild to moderate infections (predominantly respiratory tract infections) were the most commonly reported AEs. The proportion of

patients experiencing a serious infection was low and similar to interferon beta-1a or placebo, respectively. Consistent with the severity of the underlying type of MS there were more serious infections reported in both arms of the PPMS study than in the RMS studies. Pooled data from OPERA I & II and ORATORIO indicated an imbalance in malignancies in the ocrelizumab treatment group versus pooled interferon beta-1a and placebo. The only cluster that could be identified was for female breast cancer. However, incidences remained within the range of placebo data from clinical trials in MS and epidemiological data, and no firm conclusion concerning the relative risk could be made due to the low number of events and the limited follow-up period.

MS is a chronic disease requiring a lifetime treatment. CONFIDENCE is performed to assess long-term safety data (e.g. on malignancies and serious infections) of ocrelizumab in the real world setting and further characterize the safety profile in patients with multiple sclerosis newly exposed to ocrelizumab. Collected safety data will be included in the global PAS-Studies (BA39730 & BA39731). In addition, real world effectiveness data will be collected to complement the efficacy data collected in phase III studies over a long treatment duration.

Research Question and Objectives

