6.2 STUDY BACKGROUND

OCREVUS® (ocrelizumab) was approved by the United States (US) Food and Drug Administration (FDA) on March 28, 2017, as first medication for the treatment of adult patients with relapsing forms of MS (RMS) as well as PPMS (Genentech Inc., 2017). In

clinical studies ocrelizumab has demonstrated a favorable benefit/risk profile in RMS and PPMS patients (Hauser et al. 2017; Montalban et al. 2017).

The 96-week, phase 3 OPERA I & II trials reached all relevant clinical endpoints and ocrelizumab demonstrated consistent efficacy in the overall population of RMS patients. Compared with the active comparator, interferon beta-1a, ocrelizumab was associated with a significantly lower annualized relapse rate, a significantly reduced percentage of patients with disability progression confirmed at 12 and 24 weeks (both in the pre-specified pooled analysis and in each of the two phase 3 trials separately) and with an increased percentage of patients with disability improvement confirmed at 12 weeks. These findings were supported by a significantly greater suppression of brain lesions (Hauser et al. 2017).

In patients with PPMS, the phase 3 ORATORIO study demonstrated superior efficacy of ocrelizumab versus placebo with respect to the risk of confirmed disability progression at 12 and 24 weeks, ambulation speed as assessed by the timed 25-foot walk, change in the total volume of brain lesions on T2-weighted images, and change in brain volume (Montalban et al., 2017).

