8. RESEARCH METHODS

8.1 STUDY DESIGN

CONFIDENCE is a prospective, multicenter, non-interventional, long-term study collecting primary data in RMS and PPMS patients newly treated with ocrelizumab in routine clinical practice. To provide robust evidence on the safety and effectiveness profile of ocrelizumab in real-world conditions, data from 3000 MS patients from approximately 250 neurological centers and practices in Germany are planned to be included. At least 60% of the study population will be females. According to routine practice and as recommended by the German Society of Neurology (DGN Guideline 2015), visits are expected to be documented every 6 months in the main study period up to 10 years, after the initial infusions have been administered to the patient.

CONFIDENCE comprises an initial recruitment period of 30 months – which is anticipated to start in the first quarter 2018 – and will be followed by an observation period. Depending on the time point of study inclusion (i.e. start of ocrelizumab) each patient will be observed for a total duration of at least 7.5 and up to 10 years maximum, or until death / withdrawal of consent / loss to follow-up. Follow-up during the whole period is planned for all study participants, regardless of whether patients discontinue treatment with ocrelizumab or have a malignancy diagnosis. Data from CONFIDENCE will also be included in two global PAS studies (BA39730 & BA39731).

Study Flow

2000-2300 RMS patients and 700-1000 PPMS patients included in approx. 250 sites; first ocrelizumab infusion

Data collected: Informed consent, in-/exclusion criteria, patient demographics, MS disease history, MS treatment history, medical history and comorbidities, malignancy risk factor information, prior and concomitant medications, ocrelizumab administration information, vital signs, MS specific symptoms and relapses, clinical management, laboratory parameters, pregnancy status, QoL/PRO, pharmacoeconomic outcomes, JCV antibody status/index, MRI

Every ~6 months for at least 90 months (up to 10 years maximum)

Data collected: Ocrelizumab administration information, concomitant medication, AEs/SAEs/AESIs, vital signs, QoL/PRO, pharmacoeconomic outcomes, MRI, MS specific symptoms and relapse, laboratory parameters, pregnancy status, clinical management, follow-up on malignancies, treatment continuation/reasons for discontinuation (if applicable)

Study completion / Early termination visit

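### Relapse is listed only as a cumulative yes/no proportion, which grows with follow-up and cannot show whether relapse activity changes over time on drug

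*Protocol*

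**What the plan says.** Section 8.3.2 and the synopsis list one relapse-specific outcome, the "proportion of patients with relapses". Relapse also feeds treatment success, which is the "proportion of patients with no clinical disease activity measured by relapse and disease progression" and without certain treatment discontinuations, so again a yes/no score per patient. Confirmed disability progression has both a proportion and a time-to-event outcome, and disability improvement has a time-to-event outcome. Relapse has neither a rate nor a time-to-event outcome.

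The data are richer than that. The follow-up and completion lists in 8.4.2 collect "MS relapse during the treatment period (start/end dates", anticipated about every 6 months. Under 8.1, "each patient will be observed for a total duration of at least 7.5 and up to 10 years maximum", or until death, withdrawal of consent or loss to follow-up. Section 8.7.4 plans annual interim reports covering all endpoints, and 8.7.3 plans subgroup analyses of the secondary endpoints.

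Patient-year rates are specified in 8.7.1 for adverse events. Section 8.4.4 excludes effectiveness events from adverse events, so relapses do not enter those rates.

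For the pivotal RMS trials, section 6.2 reports that "ocrelizumab was associated with a significantly lower annualized relapse rate". The synopsis says that "real world effectiveness data will be collected to complement the efficacy data collected in phase III studies".

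**The concern.** The proportion of patients with at least one relapse is a function of both the relapse rate and the time observed. Within a patient it can only go from no to yes. Repeated each year in a cohort whose follow-up lengthens from about 1 year to 10, it will rise whether relapse activity is steady, falling or increasing. The same applies across subgroups or calendar cohorts with different observation times, because patients recruited early or late in the 30-month window, and those who leave early, contribute unequal periods.

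Long-term effectiveness is a stated secondary objective. Whether relapse activity holds steady, falls or rises over the years on drug is a central part of it in RMS, and the listed outcome cannot answer that. Nor can a reader set a 10-year cumulative percentage beside an annualized rate from 96-week trials. A second, smaller cost is that a patient with one relapse and a patient with several are scored alike.

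**Working it through.** **Figures in the plan.** The protocol states no relapse rate, no dispersion and no precision target for relapse. Its sample size rests on adverse events: -ln(0.05)/0.001 = 2996, which reproduces the planned 3000 but says nothing about relapse.

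**Inputs.** From 8.1: "2000-2300 RMS patients and 700-1000 PPMS patients included in approx. 250 sites", and follow-up of 7.5-10 years. Assumed: a constant relapse rate of 0.05-0.30 per patient-year, and counts that are Poisson or negative binomial with dispersion k.

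**1. Dependence on observation time.** Under Poisson the proportion with any relapse by time T is 1 - exp(-rate x T). At 0.15 per year:

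| T (years) | rate x T | proportion with any relapse |
|---|---|---|
| 1 | 0.15 | 0.139 |
| 5 | 0.75 | 0.528 |
| 7.5 | 1.125 | 0.675 |
| 10 | 1.50 | 0.777 |

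The rate is the same in every row. Even between patients with the minimum and the maximum planned follow-up, the gap is 0.777 - 0.675, about 10 percentage points, with no difference in relapse activity. At 0.05 per year the proportion runs from 0.049 (1 year) to 0.393 (10 years), and at 0.30 per year from 0.259 to 0.950. The pattern does not depend on the rate chosen.

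**2. Information kept by the yes/no cut.** With m = rate x T, the share of the count's Fisher information on the log rate that survives is m/(e^m - 1) under Poisson. For the negative binomial, p0 = (1 + km)^(-1/k) and d = m(1 + km)^(-1/k - 1). The binary information is d²/[p0(1 - p0)] and the count information is m/(1 + km). Averaged over T uniform on 7.5-10 years, the share kept is:

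| Rate per year | k = 0 | k = 0.5 | k = 1 |
|---|---|---|---|
| 0.05 | 0.80 | 0.74 | 0.70 |
| 0.10 | 0.62 | 0.57 | 0.53 |
| 0.15 | 0.48 | 0.45 | 0.43 |
| 0.20 | 0.37 | 0.37 | 0.36 |
| 0.30 | 0.20 | 0.26 | 0.28 |

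The loss is therefore about 20% to 80%. If relapses are recorded for a shorter time, less is lost. At 0.15 per year and k = 0.5, recording uniform over 1-5 years keeps 71% (29% lost), and over 1-2 years it keeps 85%.

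**3. Does the loss matter overall?** With 2000 RMS patients, T = 8.75 years and 0.15 per year (Poisson, m = 1.3125), the relative standard error of the rate is 1/sqrt(2000 x 1.3125) = 2.0% from counts and sqrt[(e^1.3125 - 1)/2000]/1.3125 = 2.8% from yes/no. Both are small.

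**4. In subgroups.** The study plans no tests, so power serves only as a yardstick for precision. Take 2150 RMS patients (the midpoint) split 60/40 into 1290 and 860, with 7.5-10 years recorded and k = 0.5. For a rate ratio of 0.85, yes/no against count gives 57% vs 79% at 0.10 per year, 60% vs 89% at 0.15 and 59% vs 93% at 0.20. For a rate ratio of 0.70, the yes/no outcome already reaches at least 94% at every rate from 0.05 to 0.30 and k from 0 to 1, against at least 98% for counts. The cut therefore costs something for modest differences and little for large ones.

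**The case against.** The strongest reply is that nothing here is misstated. The study is descriptive. The synopsis says other effectiveness data will be summarised descriptively, with time-to-event methods among those named, and full detail is left to an SAP that is not at hand. A relapse rate could appear there. To complement phase III data is also not a promise to compare on the same scale. This is fair as far as it goes: relapse is listed, not necessarily analysed, only as a proportion. But the general clause commits to no rate, and the outcome list is what the protocol fixes.

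A reader might infer that the yes/no cut throws away about half of the relapse information. The documents do not support a single figure. They give no relapse rate, and half is lost only near 0.126-0.168 per year under Poisson with 7.5-10 years observed, or at about 0.10-0.15 with overdispersion. That reading also assumes relapse recording for 7.5-10 years in every patient. Section 8.4.2 ties recording to the treatment period, observation can end early, and assessments are not mandatory.

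A reader might also infer that RMS effectiveness is estimated too imprecisely, or that subgroup contrasts always suffer materially. With 2000-2300 RMS patients the former does not hold, and the latter fails at a rate ratio of 0.70.

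**Conclusion.** The point holds as one of interpretability. A crude cumulative proportion under lengthening and unequal follow-up cannot distinguish a change in relapse activity from more time observed, and it is not on the annualized scale that the protocol itself cites. That conclusion needs no particular relapse rate. The figures of 14%, 53% and 78% at 1, 5 and 10 years illustrate it at an assumed constant 0.15 per year.

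The loss of information is secondary and conditional: about 20-80% over 0.05-0.30 per year with 7.5-10 years recorded, and about 29% at 0.15 per year (k = 0.5) with 1-5 years recorded. It matters mainly for modest subgroup differences. This is a worthwhile, inexpensive improvement to a secondary outcome. It does not affect the primary safety objective.

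**What to change.** In 8.3.2 and the synopsis, add the annualized relapse rate for RMS: documented relapses divided by patient-years in which relapses were recorded, with a 95% CI. A negative binomial model with log observation time as offset would serve. Report it overall, by year since first infusion and in the planned subgroups. Keep the "proportion of patients with relapses" as a supportive line.

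The cost is one outcome line in the protocol and one model and table in the SAP. No new data are needed, because relapse dates are already on the eCRF. A dispersion parameter has to be estimated. The denominator needs care: 8.4.2 words relapse recording by the treatment period, while 8.1 continues follow-up after discontinuation. The protocol should state which period counts, so that relapses and person-time cover the same interval.
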